3.1.3 Maximum Tolerated Dose (MTD)

The Dose Escalation Phase has concluded, and the MTD is defined as Dose Level 4 (Amendment I, version date 02/11/2020).

3.2 DRUG ADMINISTRATION

Monocytes are collected, elutriated and mixed with interferons according to [Appendix B](#).

The cell product is delivered to the inpatient ward, and infused within 4 hours after preparation. The cell product in 250 mL is infused via the intraperitoneal catheter/port over 30-60 min +/- 10 min.

After 2 cycles, per physician discretion, the infusion can be given as an outpatient in the day hospital/infusion center.

The administration is repeated every 28 days +/- 7 days to accommodate for holidays, inclement weather, or other scheduling conflicts.

Interactions between interferon gamma-1b and other drugs have not been fully evaluated. Caution should be exercised when administering interferon gamma-1b in combination with other potentially myelosuppressive agent. Preclinical studies in rodents using species-specific interferon-gamma have demonstrated a decrease in hepatic microsomal cytochrome P-450 concentrations. This could potentially lead to a depression of the hepatic metabolism of certain drugs that utilize this degradative pathway.

Peginterferon alfa-2b inhibits CYP1A2 and CYP2D6 activity. Monitor for potential increased toxicities of drugs metabolized by CYP1A2 and/or CYP2D6 with a low therapeutic index or a narrow therapeutic range when they are administered concomitantly with peginterferon alfa-2b.

Patients will continue therapy until documentation of progressive disease, limiting toxicity, intercurrent medical issues, or patient withdrawal

Participants will be contacted remotely or assessed in person at least once weekly during the first cycle of treatment. Subsequent follow up will be at least monthly, with the start of each new cycle, and then during follow up according to the defined schedule (see Study Calendar, Section [3.4](#)).

Pre-cycle and off-treatment AE assessments will be done at a scheduled clinic visit. Post-therapy follow-up assessments will be performed within 30 days of stopping study treatment over the phone or at a clinic visit.

3.3 DOSE MODIFICATIONS

3.3.1 General Management of Toxicities

- In the case of toxicity, appropriate medical treatment should be used (including anti-emetics, anti-diarrheals, etc.).
- Once a patient has a dose reduction for toxicity, the dose will not be increased.
- Participants continuing to experience toxicity at the off study visit may be contacted for additional assessments until the toxicity has resolved or is deemed irreversible.
- For AEs that are unrelated to the study drugs, study drug may be held for up to 14 days at the discretion of the PI.

3.3.2 General Recommendations for Dose Modification and Management of Hematologic Adverse Events occurring after the DLT period

Table 2. Dose Modification and Management of Hematologic Adverse Events

Observation	Action
-------------	--------

Absolute neutrophil count (ANC) \geq 1000/mcL AND Platelets \geq 75,000/mcL AND Hemoglobin \geq 8 g/dL	No interruption.
ANC < 1000/mcL OR Platelets < 75,000/mcL OR Hemoglobin < 8 g/dL	
On first occurrence, hold treatment for up to 14 days until ANC \geq 1000/mcL, platelets \geq 75,000/mcL, and hemoglobin \geq 8 g/dL. Initiate appropriate medical therapy (per Section 3.3.2.1) and no change in dose upon re-initiation.
 
On second occurrence, hold treatment for up to 14 days until ANC \geq 1000/mcL, platelets \geq 75,000/mcL, and hemoglobin \geq 8 g/dL. Initiate appropriate medical therapy (per Section 3.3.2.1). Treatment may be restarted at one dose level (DL) lower for the drug(s) causing the toxicity.
 
Patients whose counts have not recovered to ANC \geq 1000/mcL, platelets \geq 75,000/mcL, and hemoglobin \geq 8 g/dL after 14 days should be removed from treatment.

Grade 4 hematologic AE	
On first occurrence, hold treatment for up to 14 days until ANC \geq 1000/mcL, platelets \geq 75,000/mcL, and hemoglobin \geq 8 g/dL. Initiate appropriate medical therapy (per Section 3.3.2.1). Treatment may be restarted at one DL lower for the drug(s) causing the toxicity.
 
On second occurrence, discontinue all three experimental agents and follow the patient for adverse events as described in section 3.5 until resolution/stabilization of toxicity.

3.3.2.1 Hematologic toxicities

- Treatment may be delayed for a maximum of 2 weeks after holding the treatment for toxicities that develop and do not resolve as defined above (exemptions: lymphopenia, or leukopenia in the absence of grade 3 or higher neutropenia).

3.3.2.2 Neutropenia

- Growth factors to prevent neutropenia will not be administered prophylactically, but can be used to assist the recovery.
- Filgrastim/Pegfilgrastim will be used only if the patient has neutropenia with sepsis for the purpose of facilitating recovery of the neutropenic sepsis.

3.3.2.3 Thrombocytopenia

- Thrombocytopenia will be treated conservatively. In the absence of bleeding, or a necessary invasive procedure, platelet transfusions should be given for a platelet count $\leq 10,000/\text{mCL}$.
- If invasive procedure(s) is (are) planned, or the patient develops bleeding, platelet transfusions should be administered in accordance with the standard of practice, usually maintaining a platelet count above 50,000/mCL.

3.3.2.4 Anemia

- Symptomatic anemia should be treated with red blood cell transfusion and is recommended if the hemoglobin falls below 8 g/dL or the patient is symptomatic.
- The initiation of erythropoietic therapy for the management of chemotherapy-induced anemia follows the American Society of Hematology/ASCO clinical practice guidelines (<http://www.asco.org>).

3.3.3 General Recommendations for Dose Modification and Management of Non-Hematologic Adverse Events

- The management of general AEs not otherwise specified should be as per **Table 3**.
- At the discretion of the investigator, the study drugs or monocytes may be held or dose modified independently if the observed toxicity is attributed to only one of the agents, while the patient continues to receive the agent(s) not associated with the observed toxicity.
- Dose modifications for nausea, vomiting, and diarrhea will be made only if they are refractory to treatment. The time a given drug is held should not exceed 14 days.
- Asymptomatic electrolyte abnormalities with optimal repletion will not require dose reduction if resolution to grade 1 or less is documented within 72 hours.

Table 3. General Management of Adverse Events (Non-Hematologic)

Observation	Action
Grade 1 or 2 AEs resolves promptly (within 48 hours) with supportive care	Maintain dose level (DL)
Any \geq grade 3 non-hematologic $>72\text{h}$ (excluding those mentioned in Section 3.1.1 , Dosing Limiting Toxicity)	During DLT evaluation period: Patient will be removed from treatment At any other time Hold study regimen for up to 14 days until toxicity resolves to \leq grade 1. Treatment may be restarted at one DL lower according to PI discretion.

Any grade 2 non-hematologic AE lasting > 7 days despite maximal support.	Hold study regimen for up to 14 days until toxicity resolves to \leq grade 1. Treatment may be restarted at one DL lower according to PI discretion Patients whose toxicity has not resolved after 14 days will be removed from treatment.
--	--

3.3.4 Safety Protocol Stopping Rules

The study may be halted if any of the following safety conditions are met:

1. If one or more deaths occur, we will immediately stop accrual and we will promptly discuss this with the NCI IRB and the FDA. In addition, the study will be halted if any death occurs within 30 days of treatment regimen.
2. If 2 DLTs occur on dose level 1.

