2.4 TREATMENT ASSIGNMENT AND RANDOMIZATION/STRATIFICATION PROCEDURES

Cohorts

Number	Name	Description
ES1	Phase I, Dose Escalation Cohort 1	Patients with epithelial ovarian cancer, primary peritoneal cancer or fallopian tube cancer that is relapsed and platinum resistant or refractory
EX1	Dose Expansion Cohort 1	10 additional patients will be treated at the MTD

Arms

Number	Name	Description

Abbreviated Title: Phase 1 IFN + monocytes

Version Date: 12/04/2025

ES1	Phase 1, Dose Escalation Arm	The autologous monocytes cell product in 250ml total volume of investigational combination (monocytes + ACTIMMUNE + SYLATRON) is infused via the intraperitoneal catheter or port over 30-60 min +/- 10 min every 28 days +/- 7 days until disease progression, limiting toxicity, intercurrent medical issues, or patient withdrawal.
EX1	Dose Expansion Arm	10 additional patients will be treated at the MTD, defined as Dose Level 4: autologous monocytes cell product in 250ml total volume of investigational combination: Monocytes (750 x 10⁶ ± 20%) + ACTIMMUNE 50 mcg (0.2 µg/mL) + SYLATRON 250 mcg (1 µg/mL) is infused via the intraperitoneal catheter or port over 30-60 min +/- 10 min every 28 days +/- 7 days until disease progression, limiting toxicity, intercurrent medical issues, or patient withdrawal.

Randomization and Arm Assignment

Randomization and stratification procedures do not apply to this trial.

Patients in Cohort ES1 will be directly assigned to Arm ES1.

Patients in Cohort EX1 will be directly assigned to Arm EX1.

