3 STUDY IMPLEMENTATION

3.1 STUDY DESIGN

This is a single arm dose escalation study including an expansion cohort at the MTD.

A 3+3 phase I trial of monocytes with Sylatron® (Peginterferon alfa-2b) and Actimmune® (Interferon gamma-1b) dose escalation will proceed to determine the MTD. The dose-limiting toxicity (DLT) period will be during the first cycle (28 days). For each dose level, three patients will be enrolled. There will be a 2 week wait from the time of cell infusion from one patient until apheresis and cell infusion of the next patient. If any patient assigned to a particular dose level experiences DLT, then up to three additional patients (up to a total of six patients) will be enrolled at that dose level. All patients on a dose-level must complete the 28-day cycle prior to beginning enrollment on the next dose level. If any patient experiences DLT-like adverse events related to experimental agents or study procedures in subsequent cycles, enrollment will be placed on hold until evaluated by the IRB and FDA.

Following Registration Part 2, patients will have intravenous access assessment in the Department of Transfusion Medicine (DTM) Dowling Clinic and a tunneled IP catheter will be placed in interventional radiology (IR) using ultrasound guidance. The tunneled IP catheter will be placed prior to start of the protocol therapy. If the patient already has an existing IP port for prior IP chemotherapy, this can be used for IP infusion, and a new tunneled catheter will not be placed. The patient will also be given the option to have an IP port placed instead of a tunneled catheter. If she prefers the IP port, she will be evaluated and if the procedure is deemed safe and feasible, it will be performed using direct visualization in the operating room (laparoscopic camera). Research blood will be collected, and ascites will be collected if present. In the expansion cohort, solid tumor will be biopsied if amenable at the time of catheter or port placement. The purpose of the biopsy is to assess monocyte and other immune cell infiltration and differentiation related to treatment.

On Day 0, the patient will undergo intravenous line placement and apheresis in DTM. PBMCs will be stored according to standard operating procedures of DTM ([Appendix B](#)). For patients on DL1 and DL3b, there will be no Day 0 in the calendar as they will not be apheresed.

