3.1.1 Dose Limiting Toxicity

Dose-limiting toxicity (DLT) evaluation period is the first cycle. DLT is defined as:

- \geq Grade 3 fatigue (defined as fatigue not relieved by rest, limiting self-care ADLs) lasting > 7 days
- \geq Grade 3 cytopenias lasting > 7 days
- \geq Grade 3 transaminitis lasting > 7 days
- \geq Grade 3 depression lasting > 7 days
- \geq Grade 3 abdominal pain lasting > 7 days
- Any other grade ≥ 3 toxicity lasting > 72 hours despite maximal medical intervention

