3.1.2 Dose Escalation

Patients who do not complete treatment in cycle 1 for reasons other than study drug-related toxicity will be replaced. If 1 of 3 patients experiences DLT, the dose level will be expanded to 6 patients. If 2 patients in a dose level of 3 to 6 patients experience DLT, then the MTD will have been exceeded and the next lower dose level will be expanded to 6 patients. MTD will be the highest dose at which 0-1 of 6 patients experience DLT. If the planned highest dose level is reached and determined to be safe after expansion to 6 patients, it will be considered the MTD. An expansion cohort of 10 additional patients will be treated at the MTD and the results combined with those of patients at the MTD to obtain improved estimates of safety and toxicity as well as to perform analyses to address secondary objectives. If either dose level 3 or dose level 4 exceeds the MTD (≥ 2 patients on either dose level experience a DLT) then we will enroll 3-6 patients on dose level 3b.

Total Volume (250 mL)

Dose Level	Monocytes total number	SYLATRON ® Peginterferon alfa2b, mcg (final concentration)	ACTIMMUNE ® Interferon gamma-1b, mcg (final concentration)
1	0	25 mcg (0.1 μ g/mL)	5 mcg (0.02 μ g/mL)

2	$75 \times 10^6 \pm 20\%$	25 mcg (0.1 $\mu\text{g}/\text{mL}$)	5 mcg (0.02 $\mu\text{g}/\text{mL}$)
3	$750 \times 10^6 \pm 20\%$	25 mcg (0.1 $\mu\text{g}/\text{mL}$)	5 mcg (0.02 $\mu\text{g}/\text{mL}$)
3b*	0	250 mcg (1 $\mu\text{g}/\text{mL}$)	50 mcg (0.2 $\mu\text{g}/\text{mL}$)
4	$750 \times 10^6 \pm 20\%$	250 mcg (1 $\mu\text{g}/\text{mL}$)	50 mcg (0.2 $\mu\text{g}/\text{mL}$)

*DL3b will enroll if ≥ 2 subjects enrolled on DL3 or DL4 experience DLT

Number of Patients with DLT at a Given Dose Level	Escalation Decision Rule
0 out of 3	Enter up to 3 patients at the next dose level
≥ 2	Dose escalation will be stopped. This dose level will be declared the maximally administered dose (highest dose administered). Up to three (3) additional patients will be entered at the next lowest dose level if only 3 patients were treated previously at that dose.

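### With escalation closed, no rule clearly holds expansion enrollment for non-fatal cycle-1 DLTs at dose level 4

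*Combined protocol and SAP*

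**What the plan says.** Four groups of provisions in the combined protocol and SAP bear on this.

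- **Status of the trial.** Section 3.1.3: "The Dose Escalation Phase has concluded, and the MTD is defined as Dose Level 4". Section 2.4, for the expansion arm: "10 additional patients will be treated at the MTD, defined as Dose Level 4". Section 10 counts 16 patients at the MTD, 6 from escalation and 10 from expansion.
- **Stopping and holding rules.** Section 3.3.4 has two items. The first responds to deaths. The second is "If 2 DLTs occur on dose level 1". Section 3.1 adds: "If any patient experiences DLT-like adverse events related to experimental agents or study procedures in subsequent cycles, enrollment will be placed on hold", pending IRB and FDA evaluation. Section 3.1.1 fixes the window: "Dose-limiting toxicity (DLT) evaluation period is the first cycle".
- **DLT counts.** Section 3.1.2: "If 2 patients in a dose level of 3 to 6 patients experience DLT, then the MTD will have been exceeded", and "MTD will be the highest dose at which 0-1 of 6 patients experience DLT". The same section, and the footnote to its dose table, provide that level 3b will enroll if two or more patients on level 3 or level 4 have a DLT.
- **Use of the expansion data.** Section 3.1.2 wants "the results combined with those of patients at the MTD to obtain improved estimates of safety and toxicity". It gives no combined DLT count that would change the MTD.

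For the individual patient, section 3.5.1 removes those with unacceptable toxicity. The grade 3 or higher row of Table 3 carves out events named in 3.1.1, so it does not clearly cover the listed DLTs. Section 7.4.1 provides for team review and 13.1 for suspension, both without a threshold. Section 7.4.2 says no DSMB is required.

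**The concern.** The rules are uneven in a way that the protocol does not explain. One related DLT-like event in cycle 2 holds enrollment until outside bodies have looked at it. Several non-fatal DLTs in cycle 1, the window on which the MTD is defined, have no comparable hold in the expansion cohort.

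Two things are at stake. Ten of the 16 planned patients at dose level 4 enter without a clear limit on the toxicity that defines the dose, and passing with 0 or 1 DLT in 6 is weak evidence of a low rate. The primary objective is to identify the MTD. If 6 of 16 patients (38%) had a DLT, the protocol would not clearly say whether enrollment pauses or whether level 4 remains the MTD.

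**Working it through.** **1. Which rule reaches a non-fatal cycle-1 DLT in an expansion patient?**

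| Provision | Trigger | Reaches it? |
|---|---|---|
| 3.3.4 item 1 | death | no |
| 3.3.4 item 2 | 2 DLTs on level 1 | no, patients are on level 4 |
| 3.1 hold | DLT-like event after cycle 1 | no, wrong cycle |
| 3.1.2, 2 DLTs | dose level of 3 to 6 patients | no, level 4 exceeds 6 from the first expansion patient |
| 3.1.2 sentence and footnote | 2 or more on level 3 or 4 | unclear; the action is to open 3b |
| 3.5.1 | unacceptable toxicity | that patient only |
| 7.4.1, 13.1 | judgement | possible, no threshold |

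**2. The plan's own figures.** The documents give no operating characteristic for DLT monitoring in expansion. The figure a hold could affect is the 80% power in section 10 (n = 16, effect size 0.75, two-sided 0.05, paired t-test). Noncentrality is 0.75 × √16 = 3.0 on 15 df, and power is 0.801, so it reproduces. With 10 patients, noncentrality is 0.75 × √10 = 2.37 on 9 df, and power is 0.56.

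**3. What passing 0-1 of 6 shows.** P(pass) = (1−p)^6 + 6p(1−p)^5, which is 0.89, 0.66, 0.42 and 0.23 at p = 0.1, 0.2, 0.3 and 0.4. Clopper-Pearson 95% intervals are 0 to 46% after 0/6 and 0.4 to 64% after 1/6. P(4 or more DLTs in 10) is 0.013, 0.12, 0.35 and 0.62 at the same rates.

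**4. Could the 3.1.2 clause serve as the limit?** For all 16 level 4 patients at p = 0.1:

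P(2 or more of 16) = 1 − 0.9^16 − 16 × 0.1 × 0.9^15 = 1 − 0.185 − 0.329 = 0.485.

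Given that level 4 has already passed (0/6 with probability 0.531, 1/6 with 0.354), P(2 or more of 10) = 0.264 and P(1 or more of 10) = 0.651, so the figure is (0.531 × 0.264 + 0.354 × 0.651) / 0.886 = 0.42. Either way it fires too often at an acceptable rate.

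**5. The proposed hold: 2 DLTs in the first 6 or 3 in the first 9 expansion patients.**

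P(hold before the 10th) = P(2 or more of 6) + P(0 of 6) × p³ + P(1 of 6) × P(2 or more of 3).

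- p = 0.4: 0.767 + 0.047 × 0.064 + 0.187 × 0.352 = 0.835.
- p = 0.1: 0.114 + 0.531 × 0.001 + 0.354 × 0.028 = 0.125 (0.1247 unrounded, so 12%).

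| True DLT rate (assumed) | 10% | 20% | 30% | 40% |
|---|---|---|---|---|
| Held before 10th patient | 12% | 39% | 65% | 84% |
| Mean expansion patients treated, if a hold ends accrual | 9.4 | 8.0 | 6.5 | 5.1 |

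If two further patients are already in cycle 1 when it triggers, the 40% column becomes 77% with a mean of 6.8. If only 5 patients remain, a hold before the last needs 2 or more DLTs in 4: 1 − 0.6^4 − 4 × 0.4 × 0.6^3 = 0.525, or 52%, at p = 0.4, and 5% at p = 0.1.

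**6. A less sensitive alternative.** Count all level 4 patients, including the 6 from escalation, and hold at 3 of 7-9, 4 of 10-12 or 5 of 13-15. Averaged over 0/6 and 1/6 given a pass, it holds in 2%, 12% and 56% of cases at true rates of 10%, 20% and 40%.

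**The case against.** The strongest reply is that 3.1.2 already contains a rule. The level 3b sentence comes directly after the expansion-cohort sentence, is not expressly limited to escalation, and gives no denominator, and expansion patients are treated at dose level 4. Read literally, two DLTs at level 4 mean the MTD is exceeded and level 3b opens. This stands to the extent that a reader who infers that cycle-1 DLTs in expansion can trigger no stated cohort-level action at all goes further than the text. But the clause belongs to the escalation rules, its action is to enroll another level and does not hold level 4, and step 4 shows that it is unworkable as a limit for 16 patients.

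A reader might also infer that expansion patients are unmonitored. The documents do not support that. They require weekly contact in cycle 1 (3.2), SAE reports to the sponsor within 24 hours (8.3), and expedited FDA reporting of serious unexpected suspected reactions (8.7). Section 3.1 also has a two-week gap between patients, if it continues in expansion. The team may act at any time. None of these sets a DLT threshold.

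Nor do the documents show that level 4 is too toxic. They support no rate of 30-40%, and a pass favours 10% over 40% by 0.89 to 0.23, about 3.8 to 1. Finally, escalation was declared complete in an amendment dated 02/11/2020 and this version is dated 12/04/2025, so little accrual may remain. That limits the benefit without changing the reading of the text.

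**Conclusion.** The point holds as an unclear and incomplete safety rule. No provision clearly holds expansion enrollment for non-fatal cycle-1 DLTs at dose level 4, the one clause that might apply is ambiguous and has the wrong action, and no DLT proportion is given at which level 4 would cease to be the MTD. At a true rate of 40%, 4 or more of 10 expansion patients would have a DLT in 62% of cases without clearly triggering a hold; at 10% this is 1.3%. True DLT rates and the number of patients still to enroll are assumptions. The stated power and sample size are not in error. It should be corrected while any patient remains to be enrolled.

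**What to change.** 1. Add item 3 to section 3.3.4: *Expansion cohort: as soon as 2 DLTs occur among the first 6, or 3 among the first 9, expansion patients in cycle 1, enrollment stops until the IRB and FDA have evaluated the events.* This reuses the protocol's own limit (2 of 6, one third) and the hold already in 3.1.
2. State in 3.1.2 that the rule on two or more patients at level 3 or 4 applies only to the 3 to 6 escalation patients.
3. State that dose level 4 is no longer the MTD if the DLT proportion among all patients treated there is one third or more (6 or more of 16, since 16/3 = 5.3).

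Item 1 of 3.3.4 and the hold in 3.1 stay as they are.

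The cost is a short amendment with IRB approval and FDA notification, and the risk of an unnecessary pause: 12% at a true rate of 10% and 39% at 20%. If a hold ended accrual, fewer than 16 patients would remain for the correlative analysis; with 10 in total, power at effect size 0.75 falls from 80% to 56%. If false holds are the main worry, the rule in step 6 lowers them to 2% and 12%, but holds in only 56% of cases at a true rate of 40%, against 84%.

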3.4 STUDY CALENDAR

Baseline evaluations are to be conducted within 7 days prior to start of protocol therapy, unless otherwise specified. Scans and x-rays must be done within 28 days (- 7 days) prior to the start of therapy. In the event that the patient's condition is deteriorating, laboratory evaluations should be repeated within 48 hours prior to initiation of the next cycle of therapy.

1 cycle = 28 days

Procedure	Screening/ Baseline ^{15, 17}	Cycle 1 ¹						Cycle 2		Subsequent cycles	Post Therapy Follow- up ²
		Day -2 or -1	Day 0 ⁵	Day 1 ¹⁴	Day 2 ¹²	Day 27 ⁴		Day 1	Day 2 ¹²		
Clinical Assessment	X									X	X
Physical Exam		X		X	X	X		X	X	X	X
Vital signs	X	X	X	X	X	X		X	X	X	X
Performance Score	X	X				X				X	X
Offer NIH Advanced Directives Form ¹⁰	X										
Ophthalmic evaluation ⁶	X										
Tunneled IP catheter or IP port placement ⁷	X										
Venous access assessment	X										
Establish venous access prior to each apheresis			X							X	
Apheresis ¹³			X							X	
Autologous monocytes mixed with Sylatron® (Interferon Alfa-2b) and Actimmune® (Interferon Gamma-1b), IP infusion				X				X		X	
Labs (See Section 2.2 and 2.5) ¹¹	X	X		X	X	X		X	X	X	X

Procedure	Screening/ Baseline ^{15, 17}	Cycle 1 ¹						Cycle 2		Subsequent cycles	Post Therapy Follow- up ²
		Day -2 or -1	Day 0 ⁵	Day 1 ¹⁴	Day 2 ¹²	Day 27 ⁴		Day 1	Day 2 ¹²		
Research blood collection ⁸		X			X	X ³			X	X ³	
Ascites collection ⁸		X				X ³					
Biopsy (expansion) ⁸		X				X		X			X
Radiological Assessments (may include CT-C/A/P or MRI; report from outside institution is acceptable) ¹⁶	X										
Restaging imaging ⁹			Every 2 cycles							X	
Adverse Events		X	→							X	
Concomitant Medications		X	→							X	

¹Weekly phone calls will be made during cycle 1.

²Post therapy follow up will be at one month following the last dose of treatment; however, AEs due to toxicity or research will be followed until resolution to \leq grade 1. If the patient cannot return to the Clinical Center for this visit, a request will be made to collect required clinical labs (specify as needed) from a local physician or laboratory. If this is not possible, patients may be assessed by telephone for symptoms. If patient has begun another treatment regimen or palliative care, follow up may be done by telephone, and exam/labs will be omitted.

³Must be done prior to administration of study agents.

⁴Flexibility +/- 7 days permitted for Days 27-28 of each cycle.

⁵ Day 0 procedures do not apply for patients in the Dose Level 1 or Dose Level 3b cohort ⁶Ophthalmic evaluation including visual acuity and funduscopy by an ophthalmologist within 180 days (-14 days) prior to treatment.

⁷ IP catheter or port can be placed at any time prior to the start of protocol therapy. If patient has pre-existing IP catheter or IP port, this will be assessed by the clinician for determination of function within the same time frame as other baseline studies. See Section 3.1 for additional information.

⁸ Research blood, ascites and biopsy testing will be performed in the NIH laboratory, [name]. [contact].

⁹ Restaging should be performed within +/- 7 days of completion of previous cycle.

¹⁰ As indicated in section 12.3, all subjects \geq age 18 will be offered the opportunity to complete an NIH advanced directives form. This should be done preferably at baseline but can be done at any time during the study as long as the capacity to do so is retained. The completion of the form is strongly recommended, but is not required.

¹¹ CA125 lab will be drawn at the beginning of each cycle. Day 2 labs will include only CBC with differential and platelet count, unless other labs are clinically indicated.

¹² Day 2 activities apply to the first two cycles only.

¹³ Apheresis collection will be done every 1-3 months provided there is an adequate monocyte population at the time of apheresis collection. If the apheresis collection is inadequate, apheresis can be done as frequently as each cycle to obtain the desired number of monocytes.

¹⁴ Do not repeat labs if already done within 1 week.

¹⁵ Performance score (ECOG) will be performed at the beginning of each cycle.

¹⁶ MRI is performed only as clinically indicated if patient cannot tolerate CT scan with IV contrast.

¹⁷ Screening and Baseline activities will be performed according to Sections [2.2](#) and [2.5](#) respectively.

